4.4.4 Management of Temozolomide Related Adverse Events

The most common adverse reactions ($\geq 10\%$ incidence) are: alopecia, fatigue, nausea, vomiting, headache, constipation, anorexia, convulsions, rash, hemiparesis, diarrhea, asthenia, fever, dizziness, coordination abnormal, viral infection, amnesia, and insomnia.

The most common Grade 3 to 4 hematologic laboratory abnormalities ($\geq 10\%$ incidence) that have developed during treatment with temozolomide are: lymphopenia, thrombocytopenia, neutropenia, and leukopenia.

Allergic reactions have also been reported.

Please refer to [Appendix A](#) for dose modification algorithms for potential combination treatment related adverse events.

Table 0-8: Temozolomide Dosing Interruption or Discontinuation during Treatment Period

Toxicity	Temozolomide Interruption	Temozolomide Discontinuation	Reduce Temozolomide by 1 Dose Level
Absolute Neutrophil Count (ANC)	≥ 0.5 and $< 1.5 \times 10^9/L$	$< 0.5 \times 10^9/L$	≥ 0.5 and $< 1.0 \times 10^9/L$
Platelet Count	≥ 10 and $< 100 \times 10^9/L$	$< 10 \times 10^9/L$	≥ 10 and $< 50 \times 10^9/L$
NCI-CTCAE non-hematological toxicity (except for alopecia, nausea and vomiting)	Grade 2	Grade 3 or 4	Grade 3

Treatment with temozolomide may be continued when all of the following conditions are met:

- $ANC \geq 1.5 \times 10^9/L$
- Platelet count $\geq 100 \times 10^9/L$
- NCI-CTCAE non-hematological toxicity \leq Grade 1 (except for alopecia, nausea and vomiting)

Table 0-9: Temozolomide Dose Levels

Dose 0 (Assigned Starting Dose)	Dose Level 1	Dose Level 0	Dose Level -1
150 mg/m ² /day	200 mg/m ² /day	150 mg/m ² /day	100 mg/m ² /day

Please see [Appendix B](#) for Daily Dose Calculations by Body Surface Area (BSA).

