8.2.2 Warnings and Precautions

- Myelosuppression (subjects treated with temozolomide may experience myelosuppression, including prolonged pancytopenia, which may result in aplastic anemia, which in some cases has resulted in a fatal outcome).
- Myelodysplastic syndrome (cases of myelodysplastic syndrome and secondary malignancies, including myeloid leukemia, have been observed)
- Pneumocystis pneumonia (there may be a higher occurrence of PCP when temozolomide is administered during a longer dosing regimen).
- Hepatotoxicity (fatal and severe hepatotoxicity have been reported in subjects receiving temozolomide).

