40. Schiff, D., et al., Phase 1 dose escalation trial of the safety and pharmacokinetics of cabozantinib concurrent with temozolomide and radiotherapy or temozolomide after radiotherapy in newly diagnosed patients with high-grade gliomas. *Cancer*, 2016. 122(4): p. 582-7.
doi:10.1097/CAD.000000000000108

APPENDIX A - DOSE MODIFICATION ALGORITHMS FOR POTENTIAL COMBINATION TREATMENT RELATED ADVERSE EVENTS

AE Terms & Descriptions	Dose Modification Algorithms
Diarrhea	
a. Grade 1-2 (duration < 48 hr)	a. Continue Cabozantinib at the current dose. If it does not improve with supportive measures consider a dose reduction. Continue temozolomide at the current dose.
b. Intolerable Grade 2 or Grade 3	b. Interrupt Cabozantinib and temozolomide until Grade ≤ 1 then consider restarting Cabozantinib at reduced dose. Dose reduce temozolomide by one dose level for Grade 3 only. Discontinue temozolomide for grade 4.
	c. Refer to the Table 0-3 for the management of diarrhea.
Neutropenia	
a. Neutrophil count <1.5	a. Interrupt temozolomide and cabozantinib until neutrophil count $\geq 1.5 \times 10^9/L$.
b. Neutrophil count <1.0	b. Interrupt temozolomide and cabozantinib until $\geq 1.5 \times 10^9/L$. Reduce temozolomide by 1 dose level. Continue cabozantinib at the same.
c. Neutrophil count <0.5	c. Discontinue temozolomide, interrupt cabozantinib until neutrophil count is $\geq 1.5 \times 10^9/L$ then resume at same dose.
Febrile Neutropenia	
Grade 3 or 4	Interrupt temozolomide and cabozantinib until resolved. Upon resumption, reduce temozolomide by 1 dose level. Continue cabozantinib at the same dose.
Thrombocytopenia	
Grade 1 or 2	Interrupt temozolomide until $\geq 100 \times 10^9/L$. Continue cabozantinib.

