Grade 2	
 • Cabozantinib treatment may be continued if PPES is tolerated. • Cabozantinib should be dose reduced or interrupted if PPES is intolerable. • Continue urea 20% cream twice daily AND high potency steroid cream (e.g., clobetasol 0.05%) once daily and add analgesics (e.g., NSAIDs/gamma-aminobutyric acid agonists) for pain control if needed. 
Reassess at least weekly; if PPES worsens or affects self-care, proceed to the intervention guidelines for Grade 3.
 
 • Continue temozolomide at the investigator's discretion
Grade 3	
 • Interrupt cabozantinib treatment until severity decreases to Grade 1 or 0. • Continue treatment of skin reaction with high potency steroid cream (e.g., clobetasol 0.05%) twice daily AND analgesics. • Resume study drug at a reduced dose if PPES recovers to Grade ≤ 1. • Discontinue subject from study treatment if PPES does not improve within 6 weeks • Interrupt/continue temozolomide at the investigator's discretion
Proteinuria (UPCR)	
≤ 1 mg/mg (≤ 113.1 mg/mmol)	
 • No change in cabozantinib or temozolomide treatment
> 1 and < 3.5 mg/mg (> 113.1 and < 395.9 mg/mmol)	
 • Refer to Table 0-6 for the management of cabozantinib treatment. No change in temozolomide treatment
≥ 3.5 mg/mg (≥ 395.9 mg/mmol)	
 • Refer to Table 0-6 for the management of cabozantinib treatment. No change in temozolomide treatment.
Nephrotic syndrome	
 • Discontinue cabozantinib
Hepatocellular Toxicity	
Grade 2 AST or ALT or Total Bili lasting longer than a week	
 • Interrupt cabozantinib and temozolomide until Grade 1. • Refer to the Section 4.4.3.13 for the management of DILI
Other Treatment Related Adverse Events (such as fatigue, nausea, vomiting, anorexia, weight loss, etc)	

Grade 1 or Grade 2 (tolerable)	
 • Add supportive care as indicated. • Continue cabozantinib and temozolomide treatment at the current dose; monitor as clinically indicated

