Intolerable Grade 2 or Grade 3	
 • Interrupt cabozantinib and temozolomide treatment until it is a Grade 1 or tolerable grade 2. Restart both cabozantinib and temozolomide at the current dose or dose reduced by one level.^b For Grade 3 AEs related to Temozolomide dose reduce by one level. • *Note: It is recommended that dose holds be as brief as possible
Grade 4-related to temozolomide Grade 4-related to cabozantinib (except clinically non-relevant laboratory abnormalities)	
 • Discontinue temozolomide. • Subjects should have cabozantinib interrupted immediately. • Discontinue cabozantinib unless the following criteria are met: Subject is deriving clear clinical benefit as determined by the investigator Toxicity can be managed with a dose reduction following recovery to Grade 1 (or baseline) and optimal medical care
Study treatment dose adjustment is only needed if the toxicity was deemed related to cabozantinib treatment or had an unclear relationship to cabozantinib treatment. ^b except nausea, vomiting, and alopecia- no dose interruption required for temozolomide	

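### Table 0-8 assigns Grade 3 non-hematological toxicity to both stopping and reducing temozolomide, and its Grade 2 and Grade 3 rules conflict with Appendix A

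*Combined protocol and SAP*

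**What the plan says.** **Table 0-8 (Section 4.4.4).** The row headed "NCI-CTCAE non-hematological toxicity (except for alopecia, nausea and vomiting") has three entries: interrupt at Grade 2, discontinue at Grade 3 or 4, and reduce by one level at Grade 3. The conditions listed under the table let temozolomide continue only when non-hematological toxicity is Grade 1 or lower, with the same three exceptions.

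**Appendix A.**
- Diarrhea, Grade 1-2 for less than 48 hours: temozolomide continues at the current dose.
- Diarrhea, intolerable Grade 2 or Grade 3: both drugs are interrupted, followed by "Dose reduce temozolomide by one dose level for Grade 3 only. Discontinue temozolomide for grade 4".
- Other treatment-related events, Grade 1 or tolerable Grade 2: "Continue cabozantinib and temozolomide treatment at the current dose; monitor as clinically indicated".
- Other treatment-related events, intolerable Grade 2 or Grade 3: "Interrupt cabozantinib and temozolomide treatment until it is a Grade 1 or tolerable grade 2", and then "For Grade 3 AEs related to Temozolomide dose reduce by one level". A temozolomide-related Grade 4 event means discontinuation.
- Hepatocellular toxicity, only for Grade 2 lasting more than a week: "Interrupt cabozantinib and temozolomide until Grade 1". The reader is then sent to Section 4.4.3.13, where Table 0-7 gives rules for cabozantinib alone.
- Closing footnote: "Study treatment dose adjustment is only needed if the toxicity was deemed related to cabozantinib treatment", or if its relationship to cabozantinib is unclear.

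**Precedence.** Sections 4.4 and 4.4.4 both refer the reader to Appendix A. Neither says that it overrides Table 0-8.

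**The concern.** A dose-modification table should lead each event to one action. Here a Grade 3 non-hematological event leads to two incompatible ones, and the appendix that might settle the matter agrees with only one of them. A subject with tolerable Grade 2 fatigue on Day 1 of a cycle is held under Table 0-8 and dosed under Appendix A.

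The trial runs at a lead institution and four participating sites, so this will not be resolved by one team's habit. Temozolomide is half of the regimen under test, and the primary endpoint is read at 12 weeks, after three 28-day cycles. What is at stake is how consistently that regimen is delivered, and how safely it is modified. Section 4.4.4 lists diarrhea, fatigue and anorexia among the common temozolomide reactions (10% or more), so the row will be used.

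**Working it through.** The plan states no figure that depends on this row, so there is nothing to reproduce. The check is a comparison of the text, followed by dose arithmetic.

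**1. Overlap within Table 0-8**

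| Row | Interrupt | Reduce | Discontinue | Reduce and discontinue overlap? |
|---|---|---|---|---|
| ANC (×10⁹/L) | 0.5 to <1.5 | 0.5 to <1.0 | <0.5 | None |
| Platelets (×10⁹/L) | 10 to <100 | 10 to <50 | <10 | None |
| Non-hematological | Grade 2 | Grade 3 | Grade 3 or 4 | Grade 3 |

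In the two hematological rows the reduction range also lies inside the interruption range. In the non-hematological row it does not. Every cell of that row is filled and the rows above it read cleanly, so damage in text extraction is an unlikely explanation.

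**2. Table 0-8 against Appendix A (temozolomide)**

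| Event | Table 0-8 | Appendix A |
|---|---|---|
| Grade 1-2 diarrhea under 48 h | Interrupt if Grade 2 | Continue |
| Other tolerable Grade 2 (e.g. fatigue, anorexia) | Interrupt | Continue |
| Condition to restart, other events | Grade 1 or lower | Grade 1 or tolerable Grade 2 |
| Grade 3 diarrhea, or other temozolomide-related Grade 3 | Discontinue and reduce | Interrupt, then reduce |
| Grade 4, same categories | Discontinue | Discontinue |
| Grade 3 hepatic | Discontinue and reduce | No specific temozolomide rule |

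For intolerable Grade 2 events other than diarrhea, both texts interrupt and differ only in the restart condition. Section 4.8 uses tolerable Grade 2 or lower as its recovery standard, which is closer to Appendix A. Table 0-3 interrupts study treatment for Grade 2 diarrhea lasting more than 48 hours. Table 0-8 agrees with that, and any correction must keep it.

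**3. Dose consequence by week 12**

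Inputs: 150 mg/m² in Cycle 1 and 200 mg/m² from Cycle 2, Days 1-5 of each 28-day cycle (Section 4.2); levels of 200, 150 and 100 mg/m² (Table 0-9). Assumptions: the Grade 3 event follows Day 5, so that cycle's temozolomide is complete; counts allow the planned escalation; there is no later re-escalation, delay or other change.

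Planned total = 5 × (150 + 200 + 200) = 2,750 mg/m².

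| Grade 3 event in | Discontinue | Reduce one level | Difference |
|---|---|---|---|
| Cycle 1 (at 150) | 5 × 150 = 750 (27%) | 5 × (150 + 100 + 100) = 1,750 (64%) | 1,000 |
| Cycle 2 (at 200) | 5 × (150 + 200) = 1,750 (64%) | 5 × (150 + 200 + 150) = 2,500 (91%) | 750 |
| Cycle 3 (at 200) | 2,750 (100%) | 2,750 (100%) | 0 |

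The documents give no rate of Grade 3 non-hematological events for this combination, so the result is per affected subject, with no total for the trial.

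**The case against.** The best defense is that both sections send the reader to Appendix A, which is more detailed and gives a clear answer for diarrhea and other temozolomide-related events: reduce at Grade 3, stop at Grade 4. An experienced investigator would probably follow it. That is fair as a guess at intent, and it supports aligning Table 0-8 to the appendix. It does not settle the text. A cross-reference is not a precedence rule, and Table 0-8 still carries its own instruction. The appendix also leaves Grade 3 hepatic events without a temozolomide rule, although Section 8.2.2 warns that "fatal and severe hepatotoxicity have been reported in subjects receiving temozolomide". Its closing footnote, read literally, removes the need for any adjustment when toxicity is clearly due to temozolomide and not to cabozantinib.

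It can also be said that this is a drafting inconsistency with no effect on sample size or analysis. That is correct.

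A reader might infer three stronger points that the documents do not support:
- **The safety lead-in hold would be triggered differently.** The hold counts subjects who have to stop therapy in the first cycle. Temozolomide decisions would matter only if stopping temozolomide alone counted. Sections 4.6 and 5.0 speak of study treatment as a whole, and on that ordinary reading the hold is unaffected.
- **The hand-foot and blood-pressure rows of Appendix A also conflict.** Section 4.4.4 concerns temozolomide-related events, and the protocol manages these two as cabozantinib toxicities. Appendix A's blood-pressure thresholds carry no CTCAE grade.
- **Grade 3 hepatic events must end temozolomide.** Table 0-8 points both ways. Footnote a to Table 0-7 says that, with liver metastases, aminotransferase rises of less than a doubling from baseline may need no dose change if bilirubin and coagulation factors are not progressively rising. The choice is a clinical one.

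**Conclusion.** The point holds. The non-hematological row of Table 0-8 contradicts itself at Grade 3, and it conflicts with Appendix A at Grade 3 and for short-lasting or tolerable Grade 2 events. With no stated precedence, sites can act differently on the same event and all comply. For a Grade 3 event, the choice is worth 1,000 mg/m² of temozolomide by week 12 if it occurs in Cycle 1, 750 mg/m² in Cycle 2 and nothing in Cycle 3, out of 2,750 mg/m² planned. These figures rest on the timing and no-other-change assumptions above.

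The Grade 2 conflict affects dosing only if the toxicity is present when Days 1-5 are due, and it excludes nausea, vomiting and alopecia. The Simon boundaries, error rates and sample size do not depend on this row. The documents give no basis for turning the dose difference into a change in 12-week progression-free survival. This is a dosing rule that should be corrected, not a fault in the statistical design.

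**What to change.** **Table 0-8, non-hematological row**
- Discontinuation: *Grade 4*.
- Reduction by one level: *Grade 3*.
- Interruption: *Intolerable Grade 2, Grade 2 diarrhea > 48 h, or Grade 3*.
- Continuation condition below the table: *≤ Grade 1 or tolerable Grade 2 (diarrhea per Table 0-3)*, keeping the existing exceptions.

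Reduction then falls inside interruption and no longer overlaps discontinuation, as in the ANC and platelet rows.

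**Precedence.** Add under the table: *Where Appendix A gives an event-specific temozolomide rule, Appendix A governs.* This also preserves the appendix's stricter rule for Grade 2 hepatic events lasting more than a week.

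**Appendix A footnote.** Limit the closing sentence on attribution to cabozantinib dose adjustments.

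**Grade 3 hepatic events.** The investigators should set the temozolomide rule, consistent with footnote a of Table 0-7, and list it under reduction or discontinuation but not both. If they choose discontinuation, these events must also be excepted from the Grade 3 interruption entry.

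**Cost.** Three cells, one bullet, one sentence, one footnote and one clinical decision; no new data and no change to sample size or analysis. The drawback is that this is the less conservative resolution: more subjects stay on reduced temozolomide after a Grade 3 event, so the investigators must confirm it. The stricter option is to discontinue at Grade 3 in both Table 0-8 and Appendix A. On the same assumptions, that costs an affected subject 1,000 or 750 mg/m² by week 12 (Cycle 1 or Cycle 2 event), and the Grade 2 entries would still need aligning.

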Grade 3 or 4	Interrupt temozolomide and cabozantinib until $\geq 100 \times 10^9/L$. Dose reduce temozolomide by 1 dose level. Continue cabozantinib at the same dose or reduce dose by one level-at the investigator's discretion. At platelet count of $< 10 \times 10^9/L$ discontinue temozolomide.

Hypertension	
> 140 mm Hg (systolic) ^a and < 160 mm Hg OR > 90 mm Hg (diastolic) and < 110 mm Hg	
 Optimize antihypertensive therapy. Reduce cabozantinib treatment by one dose level if optimal antihypertensive therapy (usually to include 3 agents) does not result in BP <140 mm Hg systolic or <90 mm Hg diastolic. Continue temozolomide at the current dose
≥ 160 mm Hg (systolic) OR ≥ 110 mm Hg (diastolic)	
 Reduce cabozantinib by one dose level or interrupt cabozantinib treatment per investigator discretion. Re-start cabozantinib treatment at the most tolerable dose and re-escalate only if BP falls to and is sustained at < 140 mm Hg systolic and < 90 mm Hg diastolic. 
Interrupt/continue temozolomide at the investigator's discretion.

Hypertensive emergency ^a	
 Discontinue cabozantinib treatment
^a Hypertensive emergency is defined as uncontrolled elevated BP with clinical evidence of progressive or impending end-organ damage (e.g. myocardial infarction/ischemia, intracranial hemorrhage, cerebral ischemia, pulmonary edema, encephalopathy, kidney damage).	
Hand-foot Syndrome (PPES)	
Grade 1	
 Cabozantinib treatment may be continued at the current dose if PPES is clinically insignificant and tolerable. Otherwise, cabozantinib should be reduced to the next lower dose level. ^a Start urea 20% cream twice daily AND clobetasol 0.05% cream once daily. 
Reassess at least weekly; if PPES worsens at any time or does not improve after 2 weeks, proceed to the intervention guidelines for Grade 2.
 
 Continue temozolomide at the current dose.

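### Table 0-8 assigns Grade 3 non-haematological toxicity both to stopping temozolomide and to a one-level reduction, and nothing says whether the table or Appendix A governs

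*Combined protocol and SAP*

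**What the plan says.** Section 4.4.4 governs temozolomide-related toxicity. In Table 0-8, the row "NCI-CTCAE non-hematological toxicity (except for alopecia, nausea and vomiting") has three action cells: interruption at Grade 2, discontinuation at Grade 3 or 4, and reduction by one dose level at Grade 3. Below the table, "Treatment with temozolomide may be continued when all of the following conditions are met", and one of those conditions is non-haematological toxicity at Grade 1 or less, with the same three exceptions.

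Just above the table, Section 4.4.4 sends the reader to Appendix A "for dose modification algorithms for potential combination treatment related adverse events". Section 4.4 gives the same pointer for dose modifications in general. Neither states an order of precedence.

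The Appendix A entries that bear on temozolomide-related events are:

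- **Diarrhoea, intolerable Grade 2 or worse:** "Dose reduce temozolomide by one dose level for Grade 3 only. Discontinue temozolomide for grade 4".
- **Diarrhoea, Grade 1-2 lasting under 48 hours:** "If it does not improve with supportive measures consider a dose reduction. Continue temozolomide at the current dose".
- **Other treatment-related events:** temozolomide continues at a tolerable Grade 2, is reduced one level for a temozolomide-related Grade 3, and is stopped for a temozolomide-related Grade 4. After a hold, restart is allowed at Grade 1, or at Grade 2 if tolerable.
- **Hepatocellular toxicity:** the only graded entry is "Grade 2 AST or ALT or Total Bili lasting longer than a week". Section 4.4.3.13, to which it refers for drug-induced liver injury, gives dosing actions for cabozantinib only.

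**The concern.** Stopping a drug and continuing it at a lower dose are incompatible. A site that follows the discontinuation cell ends temozolomide for that subject; a site that follows the reduction cell keeps the combination going. Both follow the written protocol, so monitoring would have no deviation to find. Appendix A also shows that cabozantinib can go on alone: after neutrophils below 0.5 × 10⁹/L, temozolomide is discontinued and cabozantinib resumes. In a multicentre, single-arm trial of a two-drug combination, the regimen behind the 12-week result would then depend partly on which cell a site read.

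There is a smaller mismatch in the same row. Table 0-8 interrupts at any Grade 2 and restarts only at Grade 1 or less. Appendix A is more permissive at both steps for its block of other events, and at Grade 2 for short-lived diarrhoea.

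**Working it through.** The plan states no figure to reproduce here. The check is a comparison of cells, followed by dose arithmetic from the protocol's own schedule.

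**Step 1. Do the discontinuation and reduction cells overlap?** (Table 0-8)

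| Row | Interrupt | Discontinue | Reduce one level | Discontinue and reduce overlap |
|---|---|---|---|---|
| ANC, ×10⁹/L | 0.5 to <1.5 | <0.5 | 0.5 to <1.0 | none |
| Platelets, ×10⁹/L | 10 to <100 | <10 | 10 to <50 | none |
| Non-haematological | Grade 2 | Grade 3 or 4 | Grade 3 | Grade 3 |

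In the two blood-count rows the reduction range lies inside the interruption range, which is coherent: hold, then resume lower. Only the non-haematological row puts reduction inside discontinuation. Every cell is filled and in order, so a fault in reading the PDF is unlikely.

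**Step 2. What was probably meant?** If every Grade 3 event ended temozolomide, the Grade 3 reduction entry would have no use. The blood-count rows, the Appendix A diarrhoea entry and its block of other events all fit discontinuation at Grade 4 and reduction at Grade 3. This is inference; no sentence says it.

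**Step 3. How much temozolomide is at stake before the Week 12 scan?**

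Inputs: 150 mg/m² in Cycle 1 and 200 mg/m² from Cycle 2, Days 1-5 of 28 (Section 4.3); dose levels 200, 150 and 100 mg/m² (Table 0-9); Week 12 scan at C4D1 (Section 5.0, footnote b), so three cycles count.

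Planned: 5×150 + 5×200 + 5×200 = 750 + 1000 + 1000 = 2750 mg/m².

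Assumptions: full dose up to the event, the event after Day 5 of its cycle, recovery before the next Day 1, reduction from the dose at the event, and no re-escalation.

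- **Cycle 1 event, discontinue:** 750/2750 = 27%.
- **Cycle 1 event, reduce 150 to 100:** (750 + 500 + 500)/2750 = 1750/2750 = 64%. Gap 1000 mg/m².
- **Cycle 2 event, discontinue:** (750 + 1000)/2750 = 64%.
- **Cycle 2 event, reduce 200 to 150:** (750 + 1000 + 750)/2750 = 2500/2750 = 91%. Gap 750 mg/m².
- **Cycle 3 event after Day 5:** 2750/2750 under both readings. No gap.

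**Step 4. Sensitivity.**

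- **Reduction after a Cycle 1 event read as from the scheduled 200 mg/m²:** (750 + 750 + 750)/2750 = 2250/2750 = 82%, against 27% for discontinuation.
- **Recovery misses the next Days 1-5:** Section 4.4.4 requires Grade 1 or less before continuing, and Section 5.0, footnote j, skips missed doses. A Cycle 1 event then gives (750 + 0 + 500)/2750 = 1250/2750 = 45% under reduction, a gap of 500 mg/m². A Cycle 2 event gives (750 + 1000 + 0)/2750 = 64% under both readings, so no gap.

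For a reduction from the dose at the event, the Step 3 gaps are therefore upper bounds under the stated timing assumptions.

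**The case against.** The strongest reply is that Appendix A already settles the matter. Section 4.4 sends dose-modification decisions there, Section 4.4.4 repeats the pointer, and every subject starts on the combination. A reader who follows the pointers reaches one answer, reduce at Grade 3, for diarrhoea and for most other temozolomide-related events. Much of this stands, and it is why reduction is the likely intent. It does not remove the defect: a pointer is not a precedence rule, and the contradictory cell is still an operative instruction. For Grade 3 hepatocellular toxicity, Appendix A's dedicated block gives no temozolomide action, which leaves the contradictory Table 0-8 row as the most direct instruction.

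A reader might also infer that every difference between Table 0-8 and Appendix A is a conflict. The documents do not support that. For Grade 3 hand-foot syndrome and for blood pressure at or above 160/110, Appendix A says "Interrupt/continue temozolomide at the investigator"'s discretion; for proteinuria it says "Refer to Table 0-6 for the management of cabozantinib treatment. No change in temozolomide treatment". Tables 0-4, 0-5 and 0-6 present these as cabozantinib-associated events, whereas Table 0-8 sits in the section on temozolomide-related events. Dosing by attribution explains those rows.

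Nor can one say that both subjects necessarily stay in the main analysis. Section 6.3 keeps subjects with incorrect drug administration. It also lets the DSMC approve non-evaluable status for a subject removed from treatment before the 12-week assessment for reasons other than progression or death. Whether stopping temozolomide alone counts as removal is not stated.

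**Conclusion.** The point holds for the one row: Grade 3 carries two incompatible temozolomide instructions, and no text says which source prevails. The Grade 2 and restart differences are real but secondary. This should be corrected; it does not invalidate the design.

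The gap in planned temozolomide to Week 12 is at most 1000 mg/m² for a Cycle 1 event and 750 mg/m² for a Cycle 2 event, given reduction from the dose at the event, onset after Day 5 and recovery before the next Day 1. It is wider for Cycle 1 if the reduction is taken from the scheduled 200 mg/m², and smaller or absent if recovery is slow.

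A reader might go on to infer a bias of some size in the 12-week progression-free rate. The documents give no frequency for these events and no dose-response relation, so no such figure can be derived. The Simon error rates do not depend on this rule. The reading chosen could also affect who is counted as having to stop therapy in Cycle 1 under the lead-in hold in Section 10.3, but that section does not say whether stopping temozolomide alone counts.

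**What to change.** 1. In the non-haematological row of Table 0-8, set Discontinuation to Grade 4, set Interruption to Grade 2 or 3, and keep Reduce at Grade 3. This gives the row the same structure as the blood-count rows.
2. Add one sentence to Section 4.4.4: *Where Appendix A gives a temozolomide instruction for the event, including the Other block, Appendix A governs; otherwise Table 0-8 applies.* This also settles the Grade 2 and restart differences, so neither threshold needs rewriting.
3. Add a Grade 3 hepatocellular instruction for temozolomide to Appendix A: hold to Grade 1 or less and then reduce one level, and discontinue if the drug-induced liver injury criteria under Table 0-7 are met. The sponsor should confirm this clinically, because Section 8.2.2 warns of fatal and severe hepatotoxicity with temozolomide.

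The cost is one table row, one sentence, one appendix entry and a notice to sites, with no added subjects or visits. The downside is that subjects with Grade 3 events stay on reduced temozolomide and need continued monitoring. If the sponsor prefers discontinuation at Grade 3, the Grade 3 reduction cell should go and Appendix A should be changed to agree.

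### For temozolomide-related Grade 4 nausea or vomiting, Table 0-8 lets temozolomide continue while Appendix A stops it, and no text says which prevails

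*Combined protocol and SAP*

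**What the plan says.** Section 4.4.4 sets temozolomide actions in Table 0-8. For non-hematological toxicity the triggers are Grade 2 for interruption, Grade 3 or 4 for discontinuation and Grade 3 for a one-level reduction. The row applies to "NCI-CTCAE non-hematological toxicity (except for alopecia, nausea and vomiting"), so those three events are outside all three columns. Below the table, "Treatment with temozolomide may be continued when all of the following conditions are met": adequate neutrophils, adequate platelets, and non-hematological toxicity no worse than "Grade 1 (except for alopecia, nausea and vomiting"). That exemption also has no grade limit.

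Appendix A has a block titled "Other Treatment Related Adverse Events (such as fatigue, nausea, vomiting, anorexia, weight loss, etc"). Its row for intolerable Grade 2 or Grade 3 interrupts both drugs and restarts them at the same dose or one level lower. It then adds "For Grade 3 AEs related to Temozolomide dose reduce by one level". Footnote b, marked in that row, reads "except nausea, vomiting, and alopecia- no dose interruption required for temozolomide". In the next row, for "Grade 4-related to temozolomide", the action is "Discontinue temozolomide". Footnote b is not marked there.

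Appendix A closes with a note that adjustment is needed only when the toxicity is related, or of unclear relationship, to cabozantinib. The same sentence is footnote a of Table 0-2, which is a cabozantinib-only table.

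Sections 4.4 and 4.4.4 both refer the reader to Appendix A. Section 4.4 presents the guidance as matter to be considered, and neither section says which text governs.

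**The concern.** A dose rule for severe toxicity in a multicenter study should give one answer. Here a site working from Table 0-8 can give the next temozolomide course after a temozolomide-related Grade 4 event of nausea or vomiting, provided the counts and other toxicities allow it. A site working from Appendix A must stop the drug. A site that takes Appendix A's closing note literally could leave temozolomide unchanged even while using Appendix A.

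The events themselves are expected. Section 4.4.4 lists nausea and vomiting among temozolomide's most common reactions (10% or more), and Section 4.4.3 lists them among those seen in 20% or more of cabozantinib-treated subjects. Section 4.4 acknowledges limited clinical experience with the combination. At stake are consistent subject protection and a treatment definition that is the same at every site.

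**Working it through.** The plan states no figure on this point, so the check is a comparison of texts, followed by dose arithmetic to show the size of the gap.

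**Comparison for temozolomide-related nausea or vomiting**

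| Grade | Section 4.4.4 | Appendix A | Result |
|---|---|---|---|
| 1, or tolerable 2 | No trigger | Continue both drugs | Agree |
| Intolerable 2 | No trigger | Interruption row, with temozolomide interruption waived by footnote b | Agree on interruption |
| 3 | No trigger; may continue, dose level not stated | Interruption waived; one-level reduction sentence of unclear scope | Ambiguous |
| 4 | No trigger; may continue | Discontinue temozolomide | Conflict |

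**Grade 4.** Footnote b does not remove the conflict. It is not marked on the Grade 4 row, and its words waive interruption only, so it would not cancel a discontinuation even if it were marked there.

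**Grade 3.** The footnote b marker stands after the option to restart one level lower and before the Grade 3 reduction sentence. Its words cover interruption only, but its position leaves open whether the reduction applies to nausea and vomiting. If it does apply, the two texts can still both be followed by continuing one level lower, because the continuation rule does not fix the dose.

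**Closing note.** Read literally, it makes adjustment unnecessary for toxicity attributed to temozolomide alone. That would empty Appendix A's own temozolomide-specific Grade 3 and Grade 4 instructions.

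**Other rules that could decide the matter.** Section 4.4.3.2 offers antiemetics and supportive care. Section 4.8 stops study treatment if toxicity has not recovered to a tolerable Grade 2 or lower within six weeks, unless there is unequivocal benefit. It also lets the investigator stop treatment for an adverse event. Six weeks is 6 × 7 = 42 days and a cycle is 28 days, so another five-day course can fall due before the six-week rule applies.

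**Dose at stake at Grade 4.** Course dose = daily dose × 5 days. Daily doses at 1.0 and 2.5 m² come from Appendix B. It has no 100 mg/m² column, so body surface area × 100 is used there.

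- 200 mg/m²: 200 × 5 = 1,000 mg to 500 × 5 = 2,500 mg
- 150 mg/m²: 150 × 5 = 750 mg to 375 × 5 = 1,875 mg
- 100 mg/m²: 100 × 5 = 500 mg to 250 × 5 = 1,250 mg

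The comparison is eligibility for that full course against zero.

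**Width of the Grade 3 ambiguity.** One step in Table 0-9 is 50 mg/m². That is 50/200 = 25% or 50/150 = 33% of the dose, and 50 × 5 × 1.0 = 250 mg to 50 × 5 × 2.5 = 625 mg per course.

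**The case against.** The best case for the plan is that an exemption is not a permission. Table 0-8 takes nausea and vomiting out of a generic row and prescribes nothing for them. Section 4.4.4 points to Appendix A just above the table, every subject receives the combination, and Appendix A names these events. On that reading the table is silent and Appendix A's instruction to discontinue applies. This is a fair reading and may be what was meant. It is weakened because Section 4.4.4 does not stay silent: it states its own continuation rule and repeats the exemption inside it. A cross-reference is also not a ranking.

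Two further objections stand and limit the point. A reader might infer that the protocol lets temozolomide run on indefinitely at any grade. The documents do not support that, because the six-week rule and investigator discretion in Section 4.8 limit prolonged continuation. They leave only the immediate Grade 4 action unresolved. A reader might also infer a second contradiction at Grade 3, which the documents do not support either, given the unclear scope of footnote b.

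On the closing note, it can be said that it was carried over from Table 0-2 and may have lost its footnote marker when the PDF was read. That is possible and cannot be settled from the text. It is a reason to confine the note to cabozantinib, not a reason to leave it as it stands.

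**Conclusion.** The Grade 4 conflict holds with high confidence. The same temozolomide-related event may lead to continuation under Section 4.4.4 or discontinuation under Appendix A, and no text ranks them. The closing note adds a further, literal ground for leaving temozolomide unchanged. Grade 3 needs clarification only. The matter is worth correcting at the next amendment.

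The dose figures show how far apart the two instructions are, not how often the difference would arise. The plan gives no Grade 3 or 4 rate for nausea or vomiting on this combination. Section 1.2.4 reports that grade 3 nausea occurred in a cited 25-patient temozolomide trial, but gives no rate. A reader might be tempted to infer an effect on the 12-week progression-free rate or on a number of subjects, and nothing in the documents supports either.

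The conclusion assumes that the event is attributed to temozolomide. It also assumes that CTCAE v5.0, which is cited but not reproduced, grades at least one of the two events to 4. The point applies only to whichever it does.

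**What to change.** 1. In the non-hematological row of Table 0-8 and in the continuation condition, reword the exemption to: *except alopecia, and except nausea and vomiting below Grade 4*. Temozolomide-related Grade 4 nausea or vomiting then leads to discontinuation, as Appendix A already says.
2. Limit Appendix A's closing note to cabozantinib dose adjustment.
3. Have the clinical team state whether footnote b waives the Grade 3 one-level reduction for nausea and vomiting. The wording must keep Grade 3 nausea and vomiting out of Table 0-8's discontinuation column, which covers Grade 3 as well as Grade 4. Narrowing the exemption to interruption alone would put Grade 3 nausea or vomiting there, against any rule to reduce.

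A blanket statement that Appendix A prevails is not advised. Appendix A continues temozolomide at tolerable Grade 2 and allows restart at tolerable Grade 2. Giving it general precedence would therefore loosen Table 0-8's Grade 2 interruption and its Grade 1 resumption threshold for other non-hematological toxicities.

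The cost is a change of wording in one table row, one condition and one note, plus one clarification, with no added data or subjects. The downside is that a few subjects with Grade 4 nausea or vomiting would stop temozolomide. The clinical team should confirm the choice, since the documents do not show which text was intended.
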